11.4.3 Longitudinal Voxel-based Evaluation

The spatially normalized longitudinal FDG PET scans of each subject will be analyzed using ADMdx's NPAIRS multivariate software. Classes will be defined according to treatment or placebo condition, and visit. Example analyses are shown in Table 1 below. The output of this

evaluation will be a series of patterns showing relative increases and decreases in cerebral glucose metabolism, quantification of the placement of each subject at each time point relative to these patterns of effect, and quantification of the contribution of each pattern to the overall effect. Metrics of reproducibility and predictive power are also provided. At preference of Sponsor, group assignments may be provided in a blinded manner – that is, Group A and Group B, without designation as treatment or placebo. In the table below, to better illustrate the comparisons, they are referred to as Placebo and Treatment, but these may instead be “Group A” and “Group B.”

Table 3. NPAIRS analyses of treatment effect and stratification impact

Analysis	Group	Baseline	6 months
1	Treatment (within group only)	x	x
2	Placebo (within group only)	x	x
3	Treatment	x	x
	Placebo (both in a single analysis)	x	x
4	Treatment – mild subjects	x	x
	Treatment – later stage subjects	x	x
	Placebo – mild subjects	x	x
	Placebo – later stage subjects	x	x
5	Treatment – subjects age 50 - 65	x	x
	Treatment – subjects age >65	x	x
	Placebo – subjects age 50-65	x	x
	Placebo – subjects age >65	x	x

SPM-t contrasts will also be performed of selected groups, at thresholds of $p < 0.005$, and a cluster extent threshold of 25 voxels. These are limited to paired contrasts (e.g., baseline vs. 6 months for treatment group), or to contrasts of the difference images between baseline and 6 months, treatment vs. placebo groups. Information is more limited with regard to individual subject distribution other than at specific voxel locations.

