1.5. Application to Alzheimer's disease

The data available for PD and for AD suggest a pharmacologic profile of rasagiline compatible with either disease modification or symptomatic improvement or both. Enhanced mitochondrial function and improved dopamine neurotransmitter function would be anticipated to provide symptomatic benefit whereas the antiapoptotic neuroprotective activity of Rasagiline would be expected to provide disease modification. The proposed clinical trial will not resolve whether one or both of these important therapeutic modalities are predominant. The clinical trial is designed to demonstrate if there is enhanced metabolism in a treatment group compared to a placebo-control. The mechanism of rasagiline is highly supportive of an effect on AD with aspects such as modulation of APP metabolism uniquely relevant to AD.

2. Supporting Data

FDG PET analyses and interpretation as well as site qualification will be done by ADMdx. This section provides background information on the analytic methodology to be used in this study. Technical aspects of site qualification, scanner variables, and PET and magnetic resonance imaging (MRI) acquisition are presented in the appendix.

¹⁸F-AV-1451 Tau imaging data will be analyzed by ADMdx.

All clinical and imaging data will be integrated through a database constructed by the Alzheimer's Disease Cooperative Study (ADCS) and clinical-imaging integration analyses will be conducted in conjunction with ADCS statisticians (<http://ADCS.org>).

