9.9 MRI

A research grade (ADNI quality) MRI, acquired for each subject at the time of enrollment, will also be provided. T1, T2 and FLAIR or T2* sequence will be collected.

3D Sagittal T1 sequence: T1-weighted MPRAGE or MPRAGE-like sequence adhering to the Alzheimer’s disease Neuroimaging Initiative (ADNI) specifications. Typical scanner sequence parameters that could be used include:

Scanner	Sequence	Type	TR (ms)	TE (ms)	TI (ms)	NEX/NSA	Flip Angle(°)	Bandwidth
Siemens 3T	3D MPRAGE	(tfl)	2300	2.98	TI = 900	1	9	240 Hz/px
GE 3T	3D	IR-FSPGR	--	Min full	TI = 400	1	11	31.25 kHz
Philips 3T	3D	T1-TFE	Shortest	Shortest	TFE delay=900	1	9	Water-fat shift=1.8

All scans in this study will be evaluated using a stringent quality control procedure to ensure suitability for analysis. Quality control will be performed within 3 business days of image receipt so that in the event of an issue, the visit may be rescheduled if issues cannot be addressed through re-reconstruction. Quality control steps will include header checks, visual inspection, and quantitative inter-frame motion measurement. Image headers will be checked to ensure that the protocol was followed with regard to injected dose, injected volume, and start time after injection, number of frames, scan duration, and reconstruction parameters. Visual inspection will include checks for anatomical truncation (e.g., omission of lower slices of cerebellum), adequate image counts, and image noise such as streaking, image blur indicative of subject motion, asymmetry indicative of misalignment between emission and transmission scan, and other apparent artifacts. Quantitative motion measurement will involve calculation of the inter-timeframe translation and rotation, with preset thresholds above which a frame (or scan, if multiple frames) will not be accepted as suitable for analysis.

ADMdx has developed and will utilize an automated image processing pipeline, PETMAX™, which has secure user access, version control with back-up, and complete audit trail for use in clinical trials. PETMAX facilitates user interaction for visual inspection and quality control at multiple stages in the pipeline, and streamlines the execution of the many steps (including SPM functions) employed in image preparation and analysis. Results are logged and saved under version control.

9.10 [18F]-FDG-PET Imaging

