11.2 Statistical Methods

Intent-to-Treat (ITT) - The primary FDG analysis will include all patients who received both a screening and end of study scan of acceptable quality. The primary clinical analysis will be a modified Intent-to-Treat (mITT) approach including all patients randomized and receiving at least one post-baseline assessment.

Per-Protocol (PP) population – All Intent-to-Treat subjects who complete the study (Week 24) and have ingested between 80% and 120% of the protocol prescribed study medication as measured by pill count.

Observed case – An observed case analysis of all patients completing the study will be conducted.

LOCF – Clinical data imputation will use the LOCF approach for missing patients

Responder analysis – Responders will be defined as those that have a significant improvement on brain metabolism on FDG for the whole brain or for any of the pre-specified regions.

A secondary analysis will compare the changes in FDG at 6 months compared to the projected expected metabolism based on the Baseline FDG findings.

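### Masking of the imaging laboratory to arm is optional, and nothing fixes scan acceptance or the SUVr reference region before group assignments are released

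*Protocol*

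**What the plan says.** **Masking.** Protocol 11.4.3 describes the NPAIRS analysis, for which the laboratory needs each subject's group: "Classes will be defined according to treatment or placebo condition, and visit". On whether the labels are hidden it says only: "At preference of Sponsor, group assignments may be provided in a blinded manner". The masked option is coding as Group A and Group B. SAP 8.3 repeats the sentence. Protocol 6.6, on blinding, deals with dispensing and does not mention image analysts.

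**Who does the work.** Protocol Section 2 gives one laboratory the FDG work: "FDG PET analyses and interpretation as well as site qualification will be done by ADMdx".

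**Quality control.** Protocol 9.9 and Appendix A combine technical checks with human judgement. On the software: "PETMAX facilitates user interaction for visual inspection and quality control at multiple stages in the pipeline". On the visual part: "Visual inspection will include checks for anatomical truncation", followed by image counts, noise, blur and misalignment, none with a stated limit. Motion has a quantitative rule, "with preset thresholds above which a frame (or scan, if multiple frames) will not be accepted as suitable for analysis", but the values are not given. On timing: "Quality control will be performed within 3 business days of image receipt", so that a visit can be rescheduled if re-reconstruction does not solve the problem.

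**What depends on it.** Protocol 11.2 defines the primary set by scan quality: "The primary FDG analysis will include all patients who received both a screening and end of study scan of acceptable quality". The synopsis and SAP Section 5 do the same. Protocol 11.4.4 and SAP 8.4 name whole brain, cerebellum and pons as reference regions, but allow another to be found through NPAIRS and used.

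**The concern.** Two decisions feed directly into the primary comparison after randomisation: which Week 24 scans are accepted, and which region forms the SUVr denominator. Both involve choice. The plan allows the laboratory to hold true arm labels and sets no order between these decisions and the release of labels.

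If a scan were accepted, rejected or re-reviewed by someone who knew the arm, exclusions could depend on arm and outcome together, and randomisation would no longer protect the comparison. A reference region picked from an analysis that already separates the arms could carry the same dependence into every regional SUVr without a single scan being rejected. In a 50-patient trial with one imaging endpoint, a few such decisions matter.

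**Working it through.** **1. The order of events in the text.**
- Quality control follows image receipt within 3 business days (Protocol 9.9, Appendix A).
- SUVr values come at the end of the processing steps in Appendix A.
- Group assignments are needed for NPAIRS (Protocol 11.4.3), which takes spatially normalised images and so follows quality control.
- The natural order is therefore masked quality control first and labels later. No sentence in either document states that order, locks the accepted-scan list, or restricts re-review once labels are known.
- For the reference region the order can run the other way: NPAIRS with arm-defined classes first, then the region (Protocol 11.4.4).

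**2. The plan's own sample-size figures, to set a scale.** Protocol 11.3 gives, at two-sided 0.05, 26 per arm for 70% power and 32 per arm for 80% power at a 5% SUVr difference, and 8 per arm for 80% power at 10%. No SD is stated. With n = 2[(z(0.975) + z(power)) × SD/δ]²:
- From 32 per arm at 80%: SD = 5 / [(1.960 + 0.842) × √(2/32)] = 5/0.700 = 7.14% of mean SUVr.
- 70% power, 5%: 2 × (2.484 × 7.14/5)² = 25.2, rounded up to 26. This agrees.
- 80% power, 10%: 2 × (2.802 × 7.14/10)² = 8.0. This agrees.

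The figures are consistent with one another. The protocol does not say that this SD is that of a 24-week change, so it is used below only to translate shifts into SUVr units. The error rates do not depend on it.

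**3. Size of a selective-exclusion effect.** Inputs: 25 per arm (Protocol 11.1), no true effect, two-sample t-test at two-sided 0.05, 100,000 simulated trials. Assumptions, none given in the documents: two scans are rejected per affected arm, and the reason for rejection has correlation ρ with the outcome.

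The two lowest of 25 standard normal values average -1.965 and -1.524. Dropping them raises the mean of the remaining 23 by (1.965 + 1.524)/23 = 0.152 SD. With imperfect selection the shift is ρ × 0.152. With both arms affected in opposite directions it doubles.

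| ρ with outcome | Treated arm only: shift, two-sided error | Both arms, opposite directions: shift, two-sided error |
|---|---|---|
| 0 (blind to arm and outcome) | 0, 4.9-5.0% | 0, 4.9-5.0% |
| 0.3 | 0.05 SD, about 5.3-5.4% | 0.09 SD, about 6.2-6.3% |
| 1 (perfect ranking) | 0.15 SD, 9.4% | 0.30 SD, 23% |

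The small ranges in the 0.3 row are differences between repeated runs. At ρ = 0.5, treated arm only, the error is 5.9%. Under perfect ranking, removing one or three scans instead of two gives 6.6% or 13.5% (treated only) and 10.6% or 39.8% (both arms).

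On the plan's scale, 0.152 × 7.14 = 1.1 SUVr %, about a fifth of the 5% design difference (1.1/5 = 0.22). That is the perfect-ranking, one-arm case. At ρ = 0.3 it is 0.3 × 1.1 = 0.3 SUVr %.

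**4. The reference-region route.** The documents give nothing from which its effect on error could be calculated, so no figure is offered.

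**The case against.** The strongest reply is that the optional-masking sentence governs how groups are supplied to NPAIRS, not how scans are accepted, and that the primary endpoint is regional SUVr, analysed in 11.4.4. Quality control is rolling, within 3 business days, inside a double-blind trial. Its criteria are technical, the pipeline keeps an audit trail, and a failed scan is first re-reconstructed or rescheduled rather than dropped. To reject scans by outcome, a reviewer would need both the arm label and the computed SUVr change at a stage when neither is normally available. With seven regions and three reference regions there is not even a single outcome ranking to follow.

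Much of this stands. A reader might infer that the laboratory will judge scan quality with labels in hand, or that the primary result is biased. The documents support neither. The 9.4% and 23% figures are upper ends that require perfect selection on the outcome. Nothing in the text suggests that this would happen.

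The reply does not close the gap. The helpful ordering is inferred, not required. Later re-review is not barred. Protocol 11.1 mentions an interim analysis at 12 per arm, and if labels reached the laboratory for it, scans received afterwards would be judged with labels already held. The motion rule depends on separate time frames, and Appendix A leaves open whether the scanners can acquire them. The reference-region permission also links arm-classed output to the primary SUVr directly, so it does not matter that the masking sentence sits in the voxel section.

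**Conclusion.** The point holds as an unguarded risk to the primary endpoint. Masking is optional in both documents, and no text requires scan acceptability or the SUVr reference region to be fixed before assignments are released. Bias is not shown, and first-pass quality decisions probably come before any label.

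The possible size is modest under weak selection (about 5.3% with one arm affected, 6.3% with both, against 5%) and large only under perfect outcome ranking (9.4% and 23%). These figures rest on an assumed two rejected scans per affected arm and an assumed correlation. The documents give no rejection rate.

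A reader might also infer that choosing the existing Group A/B option would be enough. It would not: it hides the names of the arms but still shows which subjects belong together. The change is worth making because it is cheap and protects the one comparison on which the trial rests.

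**What to change.** In Protocol 11.4.3 and SAP 8.3, replace the optional wording with a required sequence:

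1. ADMdx works with subject and visit codes only, with no arm or group code, through quality control, processing and SUVr calculation.
2. The accepted-scan list, the regional SUVr values and the primary reference region (one of whole brain, cerebellum or pons) are locked and dated.
3. Group A/B codes are then released for NPAIRS.
4. True labels are released only after the NPAIRS results are filed.
5. Scan exclusions are reported by arm, with reasons.

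Protocol 11.4.4 and SAP 8.4 need a matching sentence: a reference region found through NPAIRS may be used only in a sensitivity analysis.

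The cost is wording in two documents, one dated lock step, and subject-and-visit coding, which goes further than the present A/B option. There is also a loss of flexibility, because an NPAIRS-derived reference region can no longer enter the primary analysis. No extra patients, visits or scans are needed, and NPAIRS can still be run as planned.

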11.4.4 Longitudinal Region of Interest Evaluation

The SUVr calculated for each subject will be compared using t-tests, within groups and across groups, as shown in Table 4 below. While the pre-identified reference regions for testing will be whole brain, cerebellum, and pons, an alternate reference region may be identified through the use of NPAIRS multivariate analysis and applied.

Table 4 Regions of interest for FDG analysis

Analysis	Change in FDG PET measure:	Dorso-lateral PFC	Striatum	Hip - Med temp	Anterior cingulate	Post cing-precun	Lateral temp	Inferior parietal
1	Treatment: 6m vs. screening	x	x	x	x	x	x	x
2	Placebo: 6m vs. screening	x	x	x	x	x	x	x
3	Change in treatment vs. change in placebo groups	x	x	x	x	x	x	x
4	1, 2, and 3 in substrata for	x	x	x	x	x	x	x

Analysis	Change in FDG PET measure:	Dorso-lateral PFC	Striatum	Hip - Med temp	Anterior cingulate	Post cing-precun	Lateral temp	Inferior parietal
	disease severity and age							

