STUDY DESIGN	This is a Phase II, randomized, double blind, placebo controlled, parallel group, proof-of-concept three-site study, to evaluate the effect of rasagiline in the regional brain metabolism on FDG PET. The study consists of two phases: a 24-week double blind placebo controlled treatment period and a 4-week follow-up period. Patients will be randomized to a 1:1 ratio at Baseline to receive either rasagiline or matching placebo.

	
The study drug will be given as 0.5 mg dose once daily for the first 4 weeks; it will be increased to 1 mg daily for the next 20 weeks. A total of 50 subjects will be enrolled: 25 will receive rasagiline and 25 will receive matching placebo for the 24-week treatment period.

STUDY ENDPOINTS	
Primary Endpoint
 
The primary study endpoint is the change from Baseline to Week 24 in regional glucose metabolism as measured by standard uptake units regional (SUVr) obtained through the FDG-PET.
 
Secondary Endpoints
 
 • Change from Baseline to Week 24 in ¹⁸F-AV-1451 Tau PET imaging SUVr • Change from Baseline to Week 24 on the scores of MMSE, ADAS-Cog 11 and CGIC • Change from Baseline to Week 24 on the scores of NPI and ADCS-ADL • Change from Baseline to Week 24 on the scores of Digit Span test, COWAT and QoL-AD/Study Partner • Correlation between changes in clinical measures (rasagiline vs. placebo change from baseline) and SUVr for FDG PET and SUVr for ¹⁸F-AV-1451 Tau PET • Correlation between SUVr for FDG PET and SUVr for ¹⁸F-AV-1451 Tau PET • Safety and tolerability as measured by incidence of adverse events/serious adverse events (AEs/SAEs), clinical laboratory test data, vital signs, 12-lead EKG data • Proportion of subjects with adverse events, serious adverse events and adverse events leading to discontinuation over the 24-week double blind treatment period • Proportion of subjects with laboratory abnormalities • Proportion of subjects with EKG abnormalities
SAMPLE SIZE	
Target enrollment is 50 subjects and will be recruited from three sites of the Cleveland Clinic Lou Ruvo Center for Brain Health – Las Vegas, Cleveland Main Campus and Lakewood sites

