3.3 Primary Endpoint

The primary study endpoint is the change from screening visit (baseline FDG) to Week 24 in regional glucose metabolism as measured by standardized uptake value ratio (SUV_r) obtained through the FDG-PET.

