ADMdx has developed and will utilize an automated image processing pipeline, PETMAX™, which has secure user access, version control with back-up, and complete audit trail for use in clinical trials. PETMAX facilitates user interaction for visual inspection and quality control at multiple stages in the pipeline, and

streamlines the execution of the many steps (including SPM functions) employed in image preparation and analysis. Results are logged and saved under version control.

(ii) Image Processing

Discrete timeframes for each scan will be aligned and an aggregate image created by averaging the frames. Each subject's MRI will be co-registered to the baseline PET scan, and longitudinal PET scans will be co-registered to the baseline PET scan, as well. The MRI will be segmented into gray, white, and CSF tissue images. The MRI will be spatially transformed to a target template and the PET scan(s) will be likewise transformed using the same parameters. The spatially transformed images will be intensity normalized to a mean value of 1, and smoothing applied to achieve uniform resolution with other scanners for comparison to reference data and use in the dementia classifiers. A set of template ROIs will be transformed back to the subject's native (unwrapped) brain for signal measurement in unwrapped space, with individualized masking applied using the subject's gray matter segment. The mean, standard deviation, minimum, and maximum for each ROI will be measured, as well as those in different reference regions for comparison, including whole brain without ventricles, cerebellum, and pons. This is in order to examine consistency across reference regions, and to determine whether treatment effects may influence one or more reference regions as well as target ROIs. Standardized Uptake Value Ratios (SUVrs) will be generated by taking the ratio of regions of interest to the respective reference regions.

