8.4 Longitudinal Region of Interest based Evaluation

The SUVrs calculated for each subject will be compared using t-tests, within groups and across groups, as shown in Table 4 below. While the pre-identified reference regions for testing will be whole brain, cerebellum, and pons, an alternate reference region may be identified through the use of NPAIRS multivariate analysis and applied.

9 Analysis of Clinical Measures

In general, analyses will incorporate the Intent-to-Treat principle, namely, all randomized participants will be included in the analysis. Analyses for all efficacy outcomes will be guided by exploratory analyses. All results will be reported as point estimates (odds ratios or mean differences across groups, as appropriate) and interval estimates (95% confidence intervals) with two-sided p-values denoting statistical significance. Since this is an early phase safety and preliminary efficacy study, no adjustments for multiple comparisons will be made and a p-value of 0.05 will be considered statistically significant.

All clinical measures (MMSE, ADAS-Cog11, ADCS-ADL, NPI, Digit-Span, COWAT and QoL) over 24 weeks will be analyzed using the linear mixed-effects regression model to assess the difference in the rate of change between the two treatment arms. The model will include scores as the dependent variable and time, treatment assignment, time-by-treatment interaction term and any variables determined to be confounders as independent variables. Time will be treated as a continuous variable. An unstructured variance-covariance structure will be used. A significant treatment effect will be concluded if the p-value for the time-by-treatment interaction term in the model is ≤ 0.05 . Sensitivity analyses will be conducted by analyzing the data using response profiles. Here, time will be treated as a categorical variable. The analysis of response profiles will allow us to characterize the patterns of change in the mean response over time in the treatment groups.

To assess the rate of change in the ADCS-CGIC over 24 weeks, a generalized estimating equations (GEE) model for binary data will be used. Because very few change scores were at the extreme ratings of marked worsening, moderate worsening, marked improvement, or moderate improvement are expected in this study, the ADCS-CGIC will be treated as a dichotomous dependent variable (no change/improved and worse).

The analyses will be repeated in the PP population.

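### The primary FDG endpoint names no deciding region or reference region: seven ROIs and three references are tested without ranking or error control, while the power statement covers one prefrontal comparison

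*Protocol*

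**What the plan says.** The Protocol Synopsis defines the primary endpoint as change in "regional glucose metabolism as measured by standard uptake units regional (SUVr) obtained through the FDG-PET". Protocol 3.3 defines it as change from screening to Week 24 "in regional glucose metabolism as measured by standardized uptake value ratio". Neither names a region or a reference region.

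Protocol 11.4.4 gives the analysis: "The SUVr calculated for each subject will be compared using t-tests, within groups and across groups". SAP 8.4 repeats it: "The SUVrs calculated for each subject will be compared using t-tests, within groups and across groups". Protocol Table 4 lists seven ROIs: dorsolateral PFC, striatum, hippocampus–medial temporal, anterior cingulate, posterior cingulate–precuneus, lateral temporal and inferior parietal. For each it marks a within-treatment test (analysis 1), a within-placebo test (2), a between-arm test of change (3), and repeats in severity and age substrata (4). All carry the same mark.

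Both documents list whole brain, cerebellum and pons as references and add that "an alternate reference region may be identified through the use of NPAIRS multivariate analysis and applied". Appendix A says that several references are measured "to examine consistency across reference regions, and to determine whether treatment effects may influence one or more reference regions", but gives no rule for the case where they disagree.

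The sample-size text (Protocol 11.1 and 11.3) models prefrontal cortex. For a 5% difference between two independent groups at two-tailed 0.05 it gives 26 per arm for 70% power and 32 for 80%. For a 10% difference it gives 8 per arm for 80%. The planned size is 25 per arm.

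**The concern.** A primary analysis has to say which result would meet the primary objective. Here one ROI could reach p<0.05 while six do not, or an ROI could be significant with pons as reference but not with cerebellum. The plan does not say whether the objective would then be met. The choice would be made after the results are seen, and a nominal result in any region could be presented as success.

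Two things follow. The false-positive rate of an any-region reading is above the nominal level. And the power statement, written for one prefrontal test, describes neither that reading nor a multiplicity-controlled version of it.

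Three places that might supply control do not:
- The threshold in Protocol 11.4.3 and SAP 8.3 (p<0.005 with "a cluster extent threshold of 25 voxels") applies to SPM contrasts, not to ROI t-tests.
- The SAP sentence declining multiplicity adjustment stands in Section 9, on clinical measures. If it were stretched to FDG, it would only confirm that there is no control.
- The responder definition, which accepts improvement in the whole brain or in any listed region, classifies patients. It is not a decision rule for the trial.

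**Working it through.** **1. The plan's own figures.** No SD is given. With n per arm = 2[(1.96 + z_power) × SD/Δ]² and SD solved from 32 per arm at 80% (7.14% of the mean):
- 5%, 80% power: 2 × (2.802 × 7.14/5)² = 32
- 5%, 70% power: 2 × (2.484 × 7.14/5)² = 25.2, rounded up to 26
- 10%, 80% power: 2 × (2.802 × 7.14/10)² = 8

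All three stated sizes are reproduced as a single two-sided comparison. With the noncentral t, the two 5% figures give d = 0.703 (26 per arm) and 0.711 (32 per arm). The t-based d does not return the third figure: doubling it gives 74–75% power at 8 per arm. The power figures in step 4 use d = 0.703.

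**2. False positives with one reference.** Assumptions: null drug, 25 per arm, two-sample t-tests (df 48) on Table 4 analysis 3, equal correlation among the seven ROI changes, and any ROI counts. At correlation 0 the exact values are 1 − 0.95⁷ = 30.2% two-sided and 1 − 0.975⁷ = 16.2% favourable to drug. Simulation gives the rest.

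| ROI correlation | Favourable hit | Two-sided |
|---|---|---|
| 0 | 16% | 30% |
| 0.5 | 12% | 23% |
| 0.9 | 6% | 12% |
| one named test | 2.5% | 5% |

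The favourable column is the relevant one, because the objective is improvement.

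**3. False positives with three references (7 × 3 = 21 tests).** Simulation varied ROI correlation (0–0.9), reference-change SD (0.3, 0.7 or 1.0 of the ROI-change SD) and between-reference correlation (0, 0.5 or 0.8). The favourable rate was roughly 6–29%, and the two-sided rate roughly 13–51%. A cruder model with 21 equally correlated tests gives 8–41% favourable. Its upper end assumes independence, which is unrealistic because each ROI's change enters three of the tests.

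**4. Power of the two possible repairs.** Protocol 11.3's SD reads as that of the SUVr level. For a change score with screening-to-Week-24 correlation r, d_change = d/√(2(1 − r)). At an assumed r = 0.5 the divisor is √1 = 1, so d_change = 0.703. At 25 per arm:
- Single test at 0.05: 68%.
- Bonferroni over seven (0.05/7 = 0.00714), effect confined to one ROI: 38%.
- Bonferroni over seven, same effect in all seven ROIs, at least one hit: about 79%, 69% and 56% at ROI correlation 0.5, 0.7 and 0.9.

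At r = 0.3 the single test has 54%, the per-ROI figure is 25%, and the at-least-one figures are 64%, 54% and 41%. At r = 0.7 they are 88%, 65%, and 95%, 90% and 81%.

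**The case against.** **The contrast is not really open.** A reader might infer from the equal marks in Table 4 that a within-treatment improvement alone could meet the objective. The documents do not support that. The primary objective (Protocol 3.1, SAP 3.1) compares treatment with placebo, Protocol 1.5 describes the design in the same terms, and the power text refers to two independent groups. Analysis 3 is the row that answers the objective. This part of the objection stands; what remains is that the analysis section does not mark that row as primary.

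**No any-region success rule is written down.** This is also true. The error rates above describe a reading that the plan leaves open, not one it adopts, and they rest on assumed correlations. But the plan offers no other rule, and even at ROI correlation 0.9 the favourable rate is more than double 2.5%.

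**This is a 50-patient proof-of-concept trial.** That can justify unadjusted secondary tests or a relaxed alpha. It does not remove the need to say which result meets the primary objective.

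**Correcting for seven ROIs would ruin power.** A reader might infer this from the per-ROI figure of 38%. That figure holds only for an effect confined to one ROI. For an effect shared by all seven, the chance of at least one adjusted hit can match or exceed that of the single test.

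**The alternate reference.** NPAIRS is run with arm and visit as classes: "Classes will be defined according to treatment or placebo condition, and visit". A reader might infer that the alternate reference would be tuned to the treatment contrast. The text does not say which NPAIRS analysis would supply it, so this is only a possibility. The option of coded group labels would limit choice by direction but would not remove the separation of arms.

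**Conclusion.** The concern holds for the ROI and the reference region. Neither document names the one that decides the primary objective, and no error control is stated for the ROI t-tests. It does not hold in the stronger form that no comparison is indicated, since drug versus placebo is clear from the objective.

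Nor is the sample-size arithmetic wrong. The stated sizes are reproduced for one prefrontal comparison; they simply do not describe a multi-region rule.

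If any ROI counted, a null drug would yield a favourable nominal result in about 6–16% of trials with one reference and roughly 6–29% with three, against 2.5% for one named test. These ranges depend on ROI and reference correlations that the documents do not give. The power figures also depend on the unstated r and, for the family, on how widely the effect is shared. The conclusion that a deciding ROI and reference must be named does not depend on any of these values.

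**What to change.** Before unblinding, in both documents (the SAP is still marked draft):

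1. Name Table 4 analysis 3, in one ROI and with one of the three pre-identified references, as the single primary test at two-sided 0.05. Dorsolateral PFC is the listed ROI closest to the prefrontal power model, though it is not stated to be the region modelled; the sponsor may choose another. Alternatively, keep all seven ROIs with one reference as a multiplicity-controlled family, and state its power both per ROI and for at least one hit, with the assumed r and ROI correlation.
2. Label the other ROIs, the within-group tests and the substrata as secondary. Label the other two references as consistency checks, in line with Appendix A, and the SPM and NPAIRS contrasts as supportive.
3. A lesser, conditional point: use an NPAIRS-derived reference for the primary treatment test only if it comes from pooled data without arm separation. Coded group labels do not meet that condition.

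The cost is wording; no new data are needed. Under a single primary ROI, an effect confined to another region becomes a secondary result. The controlled family avoids that, but at r = 0.5 it lowers power for an effect confined to one ROI from about 68% to 38%.
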